Title: Are Todays Continuous Glucose Monitoring Precise and Can They be Used to Reveal and Reduce Glycaemic Variability?

NCT: NCT03842683

Date: August 31th 2018

Mandatory elements to be included in access requests

Data Sharing Agreement

Please refer to the Data Sharing Agreement

Potential conflicts of interest outside the funding of the proposed research

Please refer to the Data Sharing Agreement

Funding of the proposed research

None

Research team information

[name], Senior Researcher, Steno Diabetes Center Nordjylland
[name], Head of Research at Steno Diabetes Center Nordjylland
[name], Aalborg University
[name], Head of Steno Diabetes Center Zealand

Abbreviated CV's for all team members are attached.

Research proposal information

Title of the proposed research

Are todays Continuous Glucose Monitoring precise and can they be used to reveal and reduce glycaemic variability?

Scientific rationale and relevance of the proposed research describing the objectives and the hypotheses corresponding to the objectives of the research.

Continuous Glucose Monitoring (CGM) provides an interstitial glucose reading every 5 minutes and is thus a powerful and important tool to identify glycaemic variability in people with diabetes. [1] CGM is valuable for people with diabetes to understand their glucose metabolism and it has the potential to be used for detection and prediction of glycaemic excursions, such as, the potentially fatal and inevitable events of hypoglycaemia, [2] [3] or even as a component in the holy grail of diabetes technology; the artificial pancreas. [4]

However, CGM has been criticised for being inaccurate and unreliable, amongst others, due to the physiological and a device-related delay between plasma glucose (PG) and interstitial glucose (IG). [5] [6] Nevertheless, CGM keeps on being popular and in February 2017 an international consensus was established at the Advanced Technologies & Treatments for Diabetes (ATTD) congress that even considers CGM data as a valuable and meaningful end point to be used in clinical trials of new drugs and devices for diabetes treatment where accuracy is of high importance. [7]

The above mentioned use cases entail that the CGM data are accurate. Therefore, the first part of this research proposal is to investigate whether the newest state-of-the-art CGM devices used in Novo Nordisk trials are in fact accurate. Based on these results, it is investigated to which degree glycaemic variability can be revealed.

Short lay summary of the proposed research intended for public disclosure

Use of devices for continuous monitoring of the blood sugar is valuable for people with diabetes to understand their disease and to help prevent low blood sugar. Furthermore, continuous monitoring should be used in drug development to evaluate efficacy and safety. However, the devices have been criticised for being too inaccurate. This investigation sought to reveal the inaccuracies of current devices and to assess the subsequent usability related to the mentioned use cases.

Research methodology and data (brief description of the intended method for the use of the requested data and a detailed description of the different data sources of the data that is intended to be included)

To investigate the accuracy of CGM, mean absolute relative difference (MARD) will be calculated and presented and the impact of the delay assessed by time shifting CGM measurements. Furthermore, correlation analyses, between for example, PG and first derivative of IG, will be performed to try to understand when CGM devices tend to measure inaccurate. Lastly, machine learning and/or deep learning approaches will be utilised to reveal glycaemic patterns and to detect/predict outcomes, such as, hypoglycaemia.

Different glycaemic variability investigations will be undertaken:

- Test of PG vs IG and effect on clinical research. [analysis of differences]
- Correlation between PG values at bedtime and nocturnal hypoglycaemic events [correlation analyses]
- Effect of main evening meal and meal-time dose on nocturnal hypoglycaemic events [correlation analyses]
- Prediction of PG-confirmed hypoglycaemic events with CGM, dose and meal data as input [machine learning]
- The optimal dose and meal distribution and least CGM variability / eHbA1c [machine learning]
- Algorithm to suggest optimal dosing in relation to glycaemic variability [machine learning]

Requested data are demographic, CGM, meal, dose and hypoglycaemia data from the following trial. The analyses are independent of treatment and therefore the treatment arm can be blinded.

NN1218-3854

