APPENDIX 1: ANALYSIS PLAN

More of the investigation are of an exploratory and descriptive nature without use of treatment arm and the below information is therefore not always feasible to provide.

Endpoints: Difference between PG and IG. Number of Level 1 and 2 CGM hypoglycaemic events. Time in range of CGM and PG values. Sensitivity and specificity of different models.

Analysis Set: In an intention-to-“participate” manner all non-missing data will be used in these investigations. Imputation of missing values will in some cases be necessary, see below.

Statistical models: Difference analysis will be carried out using 2-sample t-tests or more advanced models such as ANOVA or MMRM with adjustment of sex, BMI, geographical region etc. where applicable. Machine learning approaches will include models such as Kernel SVM and neural networks with PCA, SEPCOR and forward selection for feature elimination.

Transformation of data: Transformations of data will be necessary to “fit” data into the machine learning models. For example, this will include splitting up data in training and evaluation data. If data are not normally distributed, logarithmic transformation may in most cases be performed.

Handling of missing data: Multiple imputation will be used when applicable, but for signal imputation, simpler methods will be used. For example, to get pairs of CGM and glucose meter data, linear interpolation of “missing” CGM data at the time points of glucose meter data may be applied.

Multiplicity issues: For multiple hypotheses testing simple Bonferroni corrections will be made to control the type 1 errors when applicable.

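### Correlation is the only method named for the two nocturnal hypoglycaemia questions; if events are coded yes/no per night and are infrequent, it can show a several-fold risk difference as a small coefficient

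*Protocol*

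**What the plan says.** The list of investigations in the protocol (Research methodology and data) tags each item with a method. Two items concern the night. The first reads: "Correlation between PG values at bedtime and nocturnal hypoglycaemic events [correlation analyses". The second turns to food and insulin and carries the same tag: "Effect of main evening meal and meal-time dose on nocturnal hypoglycaemic events [correlation analyses".

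No coefficient type is given for either (Pearson, rank or other). Nor is it said whether the unit is the night or the person, or whether events are coded yes/no or counted.

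Appendix 1 of the SAP does not mention correlation. Its one endpoint that is a hypoglycaemic event is "Number of Level 1 and 2 CGM hypoglycaemic events", with no mention of night-time. Its statistical models are for differences: "Difference analysis will be carried out using 2-sample t-tests or more advanced models such as ANOVA or MMRM". No logistic, Poisson or other event-risk model is named, and no spline.

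The protocol also plans "Prediction of PG-confirmed hypoglycaemic events with CGM, dose and meal data as input [machine learning". Bedtime PG is not among the listed inputs of that item.

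**The concern.** A correlation between a continuous predictor and a yes/no outcome is not a risk, and its size depends on how often the event occurs. The less frequent the event, the smaller the coefficient, even when the relation between predictor and risk is unchanged. A single linear or rank coefficient also cannot describe a risk that rises at both ends of the predictor, because the two arms work against each other.

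What is at stake is how the result is read. Someone who wants to know how night-time risk changes with bedtime PG would get one small number that may correspond to a several-fold difference in risk. The second item is worded as an effect of meal and dose, and a correlation coefficient does not express one in usable units.

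**Working it through.** The documents give no event frequency, sample size, PG distribution or expected correlation, so there is no figure of the plan's own to reproduce. The mechanism was checked under stated assumptions.

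**Assumed inputs (none from the documents)**

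- Bedtime PG is log-normal with mean 9 and SD 3.5 mmol/L. On the log scale the SD is sqrt(ln(1 + (3.5/9)²)) = 0.375 and the mean is ln 9 - 0.375²/2 = 2.127.
- Each night is coded as with or without an event. A proportion p of nights has one, with p from 3% to 20%.
- logit(risk) = a - ln(OR) × PG, with a solved so that the mean risk equals p.

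**1. One strong relation.** Take OR 1.35 per mmol/L lower and p = 5%. Then ln(1.35) = 0.300 and a = -0.611.

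- At 5 mmol/L: logit = -0.611 - 1.501 = -2.112, a risk of 10.8%.
- At 12 mmol/L: logit = -0.611 - 3.601 = -4.212, a risk of 1.5%.
- r = [E(PG × risk) - 9p] / [3.5 × sqrt(p(1-p))] = -0.15, so r² is about 2%.
- The rank (Spearman) coefficient is -0.16, so changing the coefficient type does not help.

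The risks differ about sevenfold (10.8/1.5).

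**2. The same relation at different frequencies.** OR 1.2 per mmol/L lower throughout:

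| Event nights | r | AUC |
|---|---|---|
| 3% | -0.08 | about 0.65 |
| 5% | -0.10 | about 0.65 |
| 10% | -0.14 | about 0.65 |
| 20% | -0.20 | about 0.65 |

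The coefficient changes 2.5-fold (0.20/0.08) through frequency alone. The odds ratio is fixed and the AUC hardly moves.

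**3. The ceiling.** Suppose every event fell on the nights with the lowest PG. For this log-normal PG, the largest possible |r| is 9 × [p - Φ(z_p - 0.375)] / [3.5 × sqrt(p(1-p))]. That gives 0.27 at 3%, 0.33 at 5% and 0.44 at 10%. For a normal predictor the ceiling is φ(z_p)/sqrt(p(1-p)), which gives 0.40, 0.47 and 0.58. On either distribution, a coefficient judged against a maximum of 1 is misjudged.

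**4. Curvature.** For a predictor with a symmetric distribution and a risk with a symmetric U shape, both the linear and the rank coefficient are 0, whatever the depth of the U.

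**5. The other reading: counts per person.** Assume a Poisson count per person, a standardised normal PG and a rate ratio of 2 per SD lower. Then r is -0.15 at a mean of 0.05 events, -0.55 at 1, -0.71 at 3 and -0.82 at 10. The coefficient still depends on the event rate, but strong attenuation is confined to few events per unit of analysis.

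**The case against.** **The premise is not in the documents.** Neither document calls nocturnal events rare or codes them yes/no, and the SAP endpoint is a number of events. With several events per person, step 5 shows that most of the attenuation goes. This stands, and it makes the point conditional. It does not remove the point: bedtime PG varies from night to night, and one value per person would discard the night-to-night question.

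**The analyses are exploratory.** The SAP says so of much of the work, and no decision or power statement rests on r. This limits the consequence to interpretation. However, in a descriptive analysis the effect measure is the product.

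**Other planned methods can fit curvature.** The SAP states: "Machine learning approaches will include models such as Kernel SVM and neural networks". It also lists sensitivity and specificity among its endpoints. These could cover event prediction, but the prediction item does not list bedtime PG as an input, and the two nocturnal items are tagged for correlation only. The SAP's provision for non-normal data ("If data are not normally distributed, logarithmic transformation may in most cases be performed") does not remove the frequency limit of a yes/no outcome.

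**Two stronger readings are not supported.**

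- A reader might infer that a U-shaped risk would give a coefficient of the wrong sign. That depends on what is assumed at very high PG. With a quadratic log-odds centred at 10 mmol/L and 5% events, moving only the cap on the rise in log-odds from 1.5 to 4 moves r from -0.01 to +0.14. The documents say nothing about risk in that range. Only the general statement holds, that opposite arms can largely cancel.
- A reader might infer that Level 1, Level 2 and PG-confirmed events will be ranked by their correlations. No such comparison is planned, and PG-confirmed events appear only in the separate machine-learning item.

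**Conclusion.** The point holds in conditional form. Correlation is the only method named for the two nocturnal questions. The coefficient, unit and event coding are left open, and no event-risk model is named elsewhere. If nights are coded yes/no and events are infrequent, a correlation would understate the relation. Under the assumed PG distribution, a sevenfold risk difference appears as r = -0.15 at 5% event nights, and a fixed odds ratio gives coefficients that differ 2.5-fold between 3% and 20%. If numbers of events per person are meant and people have several each, the understatement is much smaller.

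The documents do not establish that the events are rare or binary, so it cannot be said that the planned analysis will mislead. The defensible conclusion is that the plan leaves this open, and that a risk model answers the question better under either coding.

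**What to change.** State the unit of analysis and the event coding for both nocturnal items, and replace the correlation tag with a model of event risk:

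- **Outcome:** any event on the night, in a logistic model with the night as unit. If numbers of events are meant, use a count model instead.
- **Repeated nights:** a person random effect, or GEE or cluster-robust standard errors. Without this the confidence bands would generally be too narrow.
- **Bedtime PG item:** a restricted cubic spline with 3 to 4 knots, reduced to a linear term if events are few.
- **Meal and dose item:** meal size and meal-time dose as predictors.
- **Reporting:** predicted risks with 95% bands, including the risk at a few pre-stated bedtime PG values, and the AUC, for each event definition used.

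The cost is a change of wording and slightly more analysis work, with a curve reported in place of one coefficient. No new data types are needed, since the request already covers CGM, meal, dose and hypoglycaemia data.

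### The claim that the analyses do not depend on treatment suits the accuracy work but is unsupported for the four dose-based investigations; a masked arm code would let it be checked

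*Protocol*

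**What the plan says.** The protocol's section on research methodology and data sets out the request as follows: "Requested data are demographic, CGM, meal, dose and hypoglycaemia data from the following trial". Treatment arm is not in that list. The next sentence gives the reason: "The analyses are independent of treatment and therefore the treatment arm can be blinded".

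The same section lists six glycaemic variability investigations. Four of them involve dose:

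- as exposure: "Effect of main evening meal and meal-time dose on nocturnal hypoglycaemic events"
- as model input: "Prediction of PG-confirmed hypoglycaemic events with CGM, dose and meal data as input"
- as the quantity to be optimised: "The optimal dose and meal distribution and least CGM variability / eHbA1c"
- as the output of an algorithm that suggests dosing.

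The other two are the correlation of bedtime plasma glucose (PG) with nocturnal events, and the comparison of PG with interstitial glucose (IG) together with its effect on clinical research.

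SAP Appendix 1 is less absolute: "More of the investigation are of an exploratory and descriptive nature without use of treatment arm". It names sex, BMI and geographical region as adjustment factors, in an open-ended list that does not mention arm. It uses all non-missing data. It specifies no arm term, arm-by-dose term, stratification by arm, between-arm contrast or sensitivity analysis by arm.

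**The concern.** To call a dose analysis independent of treatment is to assume two things. One is that a recorded dose acts alike in every arm. The other is that arm does not influence both the doses given and the risk of hypoglycaemia. The plan argues for neither.

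If the first fails, a pooled slope is an average that may describe no arm. If the second fails, arm confounds the dose-hypoglycaemia association. In either case the meal-time dose analysis could mislead, and the dosing models could learn a pattern that partly reflects arm membership. Because no arm code is requested, the data as released would not let the analysts test either assumption. The source trial already holds the variable.

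**Working it through.** The documents give no sample size, effect size, number of arms or description of the arms, so there is no planned figure to reproduce. Every input below is an assumption, chosen to show direction and order of size.

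**Step 1. Which investigations need the premise?** MARD, time-shifting and the paired PG-IG difference compare two readings from the same person at matched times, so leaving arm out is a reasonable simplification. The four dose investigations relate dose to an outcome across people and need the assumption of a common dose-response.

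**Step 2. Logistic illustration.** Two equal arms; dose has SD 1 within arm; arm B's mean dose is *m* SD above arm A's; the log-odds of nocturnal hypoglycaemia are -2 + *a*·[arm B] + *b*(arm)·dose. The pooled slope β, with intercept α, solves the logistic score equations without arm:

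½ Σ(arms) E[(p(arm, dose) - expit(α + β·dose))·(1, dose)] = 0

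| Slope A / B | *m* | *a* | Pooled slope |
|---|---|---|---|
| 0.6 / 0.2 | 0 | 0 | 0.40 |
| 0.5 / 0.3 | 0 | 0 | 0.40 |
| 0.4 / 0.4 | 0.5 | -1.0 | 0.28 |
| 0.4 / 0.4 | 0.5 | -0.5 | 0.34 |
| 0.4 / 0.4 | 0.5 | 0 | 0.40 |
| 0.4 / 0.4 | 0.5 | +0.5 | 0.45 |
| 0.4 / 0.4 | 0.5 | +1.0 | 0.50 |

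- Unequal slopes: 0.40 against 0.6 is 0.20/0.60 = 33% too low for one arm; against 0.2 it is 0.40/0.20 = 2 times too high for the other. The second row gives the same pooled value, so pooling also hides how far apart the arms are.
- Confounding by arm: against a true 0.40, the range runs from 0.12/0.40 = 30% too low to 0.10/0.40 = 25% too high. The sign follows the unknown sign of the arm effect. Adding arm to the model restores about 0.40.
- Control: a dose difference with no arm effect leaves the slope at 0.40.

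**Step 3. Closed-form check for a linear outcome.** The pooled least-squares slope is

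[(bA + bB)/2 + (m/4)(a + bB·m)] / (1 + m²/4)

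- bA = 1, bB = 0.5, m = 0: (1 + 0.5)/2 = 0.75, which matches neither arm.
- bA = bB = 1, m = 0.5, a = -0.5: [1 + 0.125 × (-0.5 + 0.5)]/1.0625 = 0.94.
- bA = bB = 1, m = 1, a = -1: [1 + 0.25 × (-1 + 1)]/1.25 = 0.80.
- bA = bB = 1, with m = 0 or a = 0: 1.00.

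So distortion needs either different slopes, or a difference in both dose and outcome.

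**Step 4. Does device bias cancel between arms?** For mean glucose it does: a bias of 0.5 mmol/L in both arms changes the arm difference by 0.5 - 0.5 = 0, whereas biases of 0.2 and 0.8 have the same average and change it by 0.6. For threshold endpoints, which SAP Appendix 1 lists, it need not. Assume normal glucose, SD 3, arm means 8.5 and 8.0 mmol/L, range 3.9 to 10:

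- No bias: time in range is Φ(0.50) - Φ(-1.53) = 62.9% and Φ(0.67) - Φ(-1.37) = 66.2%, a difference of 3.3 points.
- Bias of +0.5 in both arms: 58.6% and 62.9%, a difference of 4.3 points.
- Difference in time below 3.9: 2.3 points without bias, 1.8 points with it.

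**The case against.** The case for leaving the plan alone has real content, and several stronger readings that a reader might infer do not hold.

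- **That the dose results are biased.** The documents do not describe the arms of NN1218-3854. The harm is conditional and its direction unknown. This objection stands in full.
- **That arm is barred from the data.** The wording says that arm can be blinded, and a masked A/B code is itself a blinded arm. The SAP's partial wording and open-ended covariate list leave room for some use of arm. The protocol also defers to a Data Sharing Agreement, only part of which was available, so coded arms may be dealt with elsewhere. What remains is that neither visible text asks for a code, and that the protocol's blanket statement and the SAP's qualified one need reconciling.
- **That the PG-versus-IG investigation cannot answer its own question without a between-arm contrast.** The item reads "Test of PG vs IG and effect on clinical research. [analysis of differences", with no definition of the effect on clinical research. Paired agreement is a natural reading and needs no arm. Nor is it true that only a bias differing by arm matters: Step 4 shows an equal bias changing a time-in-range comparison. The phrase is undefined; the documents do not show it to be unanswerable.
- **That arm belongs in every machine-learning model.** The SAP's model endpoints are sensitivity and specificity, and a pooled model can be a legitimate predictor. A masked code as a required feature would tie the algorithm to an input that does not exist outside this trial.

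The SAP also calls much of the work exploratory. That lowers the stakes, but it does not supply a justification for the premise.

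**Conclusion.** The point holds in a limited form. The statement of independence from treatment is reasonable for the accuracy analyses and unsupported for the four dose investigations out of six. Under the assumptions in Step 2 (two equal arms, intercept -2, doses 0.5 SD apart where they differ), pooling could misstate a common slope of 0.4 as anything from 0.28 to 0.50, or replace slopes of 0.6 and 0.2 with 0.40. If the arms share a dose-response and do not differ in both dose and risk, nothing material is lost. The text facts are firm; the size and sign of any bias are not. The defect is that an untested assumption is made untestable by the omission of a variable that the source trial already has. A between-arm PG/IG contrast is an optional addition, depending on what the clinical-research question is meant to cover.

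**What to change.** Before data are released:

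1. Restrict the sentence on independence from treatment to the accuracy analyses (MARD, time-shifting, paired PG-IG differences), and align SAP Appendix 1 with it.
2. Add a masked arm code (A/B) to the requested data. Analysts stay blind to treatment identity.
3. In the analysis of meal-time dose and nocturnal hypoglycaemia, include arm and arm-by-dose terms, or stratify by masked arm.
4. For the machine-learning dose models, report performance by masked arm as a sensitivity check. Do not make arm a required feature.
5. Define the clinical-research question. If it covers treatment comparisons, report the A-minus-B difference in mean glucose, time in range and hypoglycaemic events by PG and by IG, noting that an equal bias can still move the threshold endpoints. If not, state that it is limited to paired agreement.

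The cost is one more variable in the request, one or two model terms, and slightly wider intervals if the arms do not differ. No new data collection is needed.

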APPENDIX 1: ANALYSIS PLAN

More of the investigation are of an exploratory and descriptive nature without use of treatment arm and the below information is therefore not always feasible to provide.

Endpoints: Difference between PG and IG. Number of Level 1 and 2 CGM hypoglycaemic events. Time in range of CGM and PG values. Sensitivity and specificity of different models.

Analysis Set: In an intention-to-“participate” manner all non-missing data will be used in these investigations. Imputation of missing values will in some cases be necessary, see below.

Statistical models: Difference analysis will be carried out using 2-sample t-tests or more advanced models such as ANOVA or MMRM with adjustment of sex, BMI, geographical region etc. where applicable. Machine learning approaches will include models such as Kernel SVM and neural networks with PCA, SEPCOR and forward selection for feature elimination.

Transformation of data: Transformations of data will be necessary to “fit” data into the machine learning models. For example, this will include splitting up data in training and evaluation data. If data are not normally distributed, logarithmic transformation may in most cases be performed.

Handling of missing data: Multiple imputation will be used when applicable, but for signal imputation, simpler methods will be used. For example, to get pairs of CGM and glucose meter data, linear interpolation of “missing” CGM data at the time points of glucose meter data may be applied.

Multiplicity issues: For multiple hypotheses testing simple Bonferroni corrections will be made to control the type 1 errors when applicable.

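### Time in range is listed for CGM and PG but not tied to matched readings; if the two are compared, test timing could imitate or hide device disagreement

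*SAP*

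**What the plan says.** SAP Appendix 1, Endpoints, names "Time in range of CGM and PG values" without saying which CGM readings enter the CGM figure. Under Analysis Set, "all non-missing data will be used in these investigations", with the addition that "Imputation of missing values will in some cases be necessary, see below". Under Statistical models, "Difference analysis will be carried out using 2-sample t-tests or more advanced models such as ANOVA or MMRM".

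Pairing appears once, under Handling of missing data. There, "to get pairs of CGM and glucose meter data", linear interpolation of CGM "at the time points of glucose meter data may be applied". It is an optional example and is not linked to time in range. From this text I take PG to be the glucose-meter value.

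The Protocol (Scientific rationale) describes CGM as giving a value at 5-minute intervals, and it cites a delay between plasma and interstitial glucose. Its section on research methodology and data plans MARD, time shifting of CGM, and this item: "Test of PG vs IG and effect on clinical research. [analysis of differences". Another item there uses PG values at bedtime. No meter schedule is given.

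**The concern.** The two time-in-range figures can rest on different sets of moments. A full CGM trace weights every part of the day equally, whereas PG is seen only when someone tests. If test times are related to glucose, the two figures differ even when the sensor is perfect. Read literally, the plan allows this comparison.

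Two things are at stake, both confined to the time-in-range conclusion:

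- A gap could be read as a device effect when part or all of it comes from when people tested. Equally, a real disagreement could be cancelled by test timing.
- A 2-sample t-test on per-person figures treats them as independent although each person supplies both. With positively correlated figures it could miss a real difference.

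**Working it through.** The documents state no time-in-range value, sample size or power, so there is no figure to reproduce. The checks below show the mechanism. Every input apart from the 5-minute interval is an assumption. All gaps are PG minus CGM in percentage points.

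**1. Closed form, error-free sensor, full trace.** Let p be true time in range and k the testing rate per unit time in range relative to out of range. Then gap = kp/(kp + 1 - p) - p.

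- p = 0.60, k = 0.8: 0.48/0.88 - 0.60 = -5.5
- p = 0.60, k = 1: 0.0
- p = 0.60, k = 1.25: 0.75/1.15 - 0.60 = +5.2
- p = 0.50 to 0.70: -5.6 to -4.9 for k = 0.8, and +4.5 to +5.6 for k = 1.25

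Test times unrelated to glucose add noise but no bias.

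**2. Simulated days.** Assumed: 100 people, 14 days, 288 CGM points a day, range 3.9-10 mmol/L, base glucose 7.5 mmol/L, and three meals with a rise of 2 or 4 mmol/L. The sensor is either error-free or has 12% noise with 5% bias. Each cell gives the results for a rise of 2, then 4.

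| Assumed test times | Error-free, full trace | Error-free, matched | Noise and bias, full trace | Noise and bias, matched |
|---|---|---|---|---|
| 4 a day: pre-meal, bedtime | +6.5, +17.2 | 0.0, 0.0 | +16.4, +23.9 | +8.8, +8.9 |
| 7 a day: pre-meal, post-meal, bedtime | -3.7, -8.0 | 0.0, 0.0 | +4.5, 0.0 | +7.9, +6.2 |
| 3 a day: post-meal | -20.8, -45.0 | 0.0, 0.0 | -12.6, -36.4 | +8.0, +3.0 |

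The error-free columns show timing imitating disagreement. With seven tests and a rise of 4, the full-trace gap is 0.0 while the matched gap is +6.2, so timing hides disagreement. With post-meal tests the full-trace gap even has the opposite sign to the matched one.

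A second simulation used 200 people, 14 days, and four assumed profiles with true time in range from 42.5% to 70.1%. With an error-free sensor and the full trace, random times gave -0.1 to +0.2, pre-meal plus bedtime +7.3 to +15.1, and seven-point -5.5 to -3.3.

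**3. What matching does not remove.** In the second simulation, a pure 10 to 15 minute delay was made the only sensor error. Full-trace CGM time in range changed by 0.0. The matched gap was:

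- random times: -0.3 to +0.3
- pre-meal plus bedtime: +0.2 to +1.2
- seven-point: +0.7 to +1.7
- 45 minutes after meals: -5.1 to -2.3

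A 10-minute shift restored 0.0 when the delay was 10 minutes. It left -1.3 to +0.8 when the delay was 15 minutes, and it created -1.3 to +1.2 when there was no delay.

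**4. Ignoring the pairing.** Take equal variances and correlation r between a person's PG and CGM figures. The 2-sample standard error is 1/sqrt(1 - r) times the paired one. When the paired test has 80% power, the 2-sample test has power Phi(2.80 - 1.96/sqrt(1 - r)).

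- r = 0.3: ratio 1.20, power 68%
- r = 0.5: ratio 1.41, power 51%
- r = 0.7: ratio 1.83, power 22%

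**5. Precision cost of matching.** With 4 tests a day for 14 days, 4 x 14 = 56 CGM readings are used instead of 288 x 14 = 4,032. At 60% in range, with independent readings, the per-person standard error is sqrt(0.6 x 0.4/56) = 6.5 points. This applies to the matched CGM level, not to the paired difference.

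**The case against.** The strongest reply is that the plan commits to none of this. It does not say that the two figures will be contrasted, that the full trace will be used, or that a gap will be read as sensor error. It also opens with the statement "More of the investigation are of an exploratory and descriptive nature". That stands, and it makes the point conditional.

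Four further arguments carry weight:

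- **The sampling difference may be the question.** The Protocol item also concerns the effect on clinical research. What a trial would report from full CGM rather than meter tests is a legitimate target, and sampling is then part of the answer. Even so, the sampling part should be visible separately.
- **Accuracy is covered elsewhere.** MARD, time shifting and the PG-IG difference do not have the sampling problem. A reader might infer that the study's accuracy conclusions as a whole are compromised; the documents do not support that.
- **MMRM is on the list.** It can handle two figures per person, so the pairing problem arises only if the 2-sample test, which is named first, is the one used.
- **The magnitudes are assumed.** The two simulations give error-free gaps of -5.5 to +15.1 and -45.0 to +17.2, which shows how far they depend on the chosen schedule and profile. The bedtime item shows that some PG values are tied to time of day, not that test times in this study were related to glucose.

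What the reply does not remove is that the only pairing rule is optional and is not attached to this endpoint. A confounded gap misleads in descriptive work too.

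**Conclusion.** The point holds in conditional form. If the two time-in-range figures are compared under the rules as written, test timing is mixed with CGM-meter disagreement whenever test times are related to glucose, and a 2-sample t-test ignores the within-person link. Comparison at matched times within person is a better method and costs little, so the change should be made. The risk is limited to the time-in-range conclusion.

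Size and sign for this study cannot be given. The -5.5 and +5.2 points rest on assumed p and k, the simulated gaps on assumed profiles, schedules and range, and the power losses on assumed r.

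Two stronger readings should be avoided. One is that the plan will in fact make the full-trace comparison; it is only permitted. The other is that matching isolates sensor error. The matched difference also contains delay, meter error and interpolation error, and it still depends on when people tested.

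The conclusion rests on the Protocol and SAP Appendix 1. The Protocol refers to the Data Sharing Agreement for its analysis plan, and I have not seen the agreement text ahead of that appendix.

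**What to change.** In SAP Appendix 1, state whether the two time-in-range figures will be compared. For any such comparison:

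- Compute both figures at the same meter times, using the interpolation already described.
- Analyse them within person, by a paired test or a GEE or mixed model clustered by person, in place of a 2-sample t-test.
- Report full-trace CGM time in range alongside as descriptive.
- If full CGM versus meter sampling is the question, report two parts that sum to PG minus full CGM. The first is CGM at meter times minus full CGM (sampling). The second is PG minus CGM at meter times (CGM-meter disagreement at the tested times).
- State that the second part includes sensor error, delay, meter error and interpolation error, and depends on the test schedule.
- Treat any time-shifted repeat as a sensitivity analysis only, since a shift that does not match the true delay can itself create a gap of about 1 point in the illustration.

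The cost is SAP wording and one derived dataset; the interpolation and the time shift are already planned. The drawback is that the matched figures use fewer CGM readings and are less precise.
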